13.2 Independent Data Review and Event Adjudication

To meet the trial's ethical responsibility to its subjects, results will be monitored by two independent groups that have no formal involvement with the subjects or the investigation, as follows:

1. DSMB- Data Safety Monitoring Board.
2. CEC- Clinical Events Committee.

The members of these committees shall function independently of Endotronix and the CRO.

13.2.1 DSMB and CEC Composition

These two committees will include a Data Safety Monitoring Board (DSMB) and Clinical Events Committee (CEC). Each committee will be composed of at least three or more members (at least two physicians from the fields of HF cardiology and Interventional Cardiology) who are not directly involved in the conduct of the trial. A semi-annual report will be provided to the FDA, which will include the names of each DSMB and CEC member.

13.2.2 DSMB

The DSMB will review the study at key points during the conduct.

The first DSMB safety review will take place after the first 50 subjects which have been implanted with the Cordella PA Sensor reached their Month 3 follow-up. The next DSMB

safety will then take place after the first 100 implanted subjects reached their 30-day follow-up.

Periodic safety review of study data every six months from the date of the first Cordella PA Sensor implant. Members will be provided data summaries (listings) from the clinical study in a blinded fashion without site or physician identification. Based on the safety data, the DSMB may recommend that the trial be modified or stopped. No formal statistical rule will be defined for stopping the trial for safety reasons.

The DSMB process (including their ability to stop an ongoing study due to safety concerns) is documented in the study specific DSMB Charter.

13.2.3 CEC

The CEC will adjudicate all events including device malfunctions dynamically. Each event will be adjudicated by an independent CEC committee (at least 3 reviewers) with the final adjudicated result being a consensus of the committee.

The CEC process is documented in the study specific CEC Charter.

13.3 Quality System, Audit and Inspection

13.3.1 Quality system

Endotronix is responsible for implementing and maintaining quality assurance and quality control systems with written Standard Operating Procedures. Endotronix/the CRO is responsible for ensuring that all parties involved with the trial agree to direct access to all trial-related sites, source data and documents, and reports for the purposes of monitoring and auditing by Endotronix/the CRO, and inspection by domestic and foreign regulatory authorities.

The documentation of the trial should be adequate for reconstruction of the course of events (audit trail).

13.3.2 Audit

An audit is the systematic and independent examination of trial-related activities and documents to determine whether the evaluated trial-related activities were conducted, and the data recorded, analyzed and accurately reported according to the protocol/ CIP, Endotronix /the CRO's Standard Operating Procedures, GCP and applicable regulatory requirements.

The Investigator will permit an appointed person by the Quality Assurance Unit of Endotronix/the CRO to audit the facilities and documentation at agreed times. Auditors are independent of the clinical trial and its performance.

13.3.3 Inspection

Inspection is the act by regulatory authorities of conducting an official review of the documents, facilities, records and other resources that are deemed by the authorities to be related to the clinical trial and that may be located at the trial site, at Endotronix, at the CRO, or at other facilities deemed appropriate by the regulatory authorities. The Investigator is obliged to cooperate with any inspection.

13.4 Maintenance of Study Documentation

The Investigator must maintain the following documents throughout the study:

- Protocol/ CIP
- IRB/ IEC Approvals and Correspondence
- IRB/ IEC Approved ICF
- Correspondence with Endotronix
- Electronic Signature Authorization Form Device Accountability
- Investigator Agreements
- Curriculum Vitae
- Financial Disclosure Forms
- Telephone Logs
- Screening Logs
- eCRFs
- Monitoring Visit Log
- Laboratory Accreditation and Normal Values
- Site Delegation and Responsibility log
- Source Documents supporting information on eCRFs
- Any other study specific documents

13.5 Subject Data Protection

Subjects will be identified on the eCRF by a subject identification number. The investigator will maintain a confidential subject identification list separate from investigational files to link medical records and subject identification numbers.

All information and data sent to Endotronix or their authorized representative, concerning subjects or their participation in this study, will be considered confidential. All data used in analysis and

reports will be used without identifiable reference to the subject. At all times throughout the study, confidentiality shall be observed by all parties involved. All data shall be secured against unauthorized access.

All subjects consented for this study will be informed and must agree to the use and disclosure of their study information by the institution and investigators to Endotronix, their agents and representatives, the Competent Authorities (CAs) or other government agencies or review boards.

13.6 Protocol/ CIP Modifications

Changes to the protocol/ CIP during the trial will be documented as amendments. The amended protocol will be signed by the relevant personnel at Endotronix, and by the Investigator(s).

Depending on the contents of the amendment and local legal requirements, the amendment will be submitted to the relevant IRBs/ IECs and, where necessary, to the FDA/ national CAs of the participating EU member states.

The Investigator should not implement any deviation from, or changes to the protocol, without agreement by Endotronix and the CRO and prior review and documented approval/favorable opinion of the appropriate IRB/ IEC and, if legally required, the FDA/ CA, except where necessary to eliminate an immediate hazard to the subjects, or when the change(s) involve only logistical or administrative aspects of the trial.

If an amendment substantially alters the trial design, increases the potential risk to the subjects or affects the treatment of the subject, then the Information Sheet must be revised and submitted to the relevant IRB/ IEC and, where necessary, to the FDA/ national CAs of the participating EU member states, for review and approval. When a subject is currently undergoing trial procedures and is affected by the amendment, then the subject must be asked to consent again using the new Information Sheet. The new Information Sheet must be used to obtain consent from new subjects before enrollment.

In general, any substantial amendment to the CIP will be approved by the relevant IRB/IEC and, where necessary, by the FDA / national CAs of the participating EU member states before it can be implemented.

13.7 Compliance/ Investigational Site Termination

13.7.1 Compliance

Compliance is the adherence to all trial-related requirements, to Good Clinical Practice (GCP) and to regulatory rules and regulations.

13.7.2 Investigational Site Termination

An initiative for center closure or study termination can be taken at any time either by the sponsor or by the investigator, provided there is reasonable cause and sufficient notice is given in advance of the intended termination. Endotronix reserves the right to terminate an investigational site from the study for any of the following reasons:

- Repeated failure to complete case report forms
- Failure to obtain ICF
- Failure to report SAEs and UADEs/ USADEs
- Loss of or unaccountable investigational device inventory
- Repeated protocol/ CIP violations
- Failure of investigator to comply with training or Instructions for Use
- Failure to screen and/or enroll an adequate number of subjects
- Insufficient subject and caregiver/Companion training

13.8 Record Retention

Endotronix and all participating Investigators must establish and maintain records and reports. The Investigator must maintain the signed ICFs, eCRFs, study documentation (listed above) and source documents for at least 15 years from the date of the manufacture of the last product in agreement with the local regulations. Endotronix should be contacted if the Principal Investigator plans to leave or otherwise absent themselves from the investigational site.

In the event of an FDA/ CA audit, the Investigator must allow FDA/ CA access to the study records for inspection and copying. The Investigator must inform Endotronix of any FDA/ CA audit and provide Endotronix with a copy of Form FDA 483/ List of Observations, if issued.

The trial master file, the eCRFs, and other material supplied for the performance will be retained by Endotronix according to applicable regulations and laws.

13.9 Site Training

Sites will be trained by Endotronix on the device usage and on implant technique as appropriate. Training on GCP, protocol required procedures and data collection will be provided by the vendor(s).

13.10 Confidentiality of trial results

The results of this trial are confidential and are not to be transmitted to a third party in any form or fashion. All persons involved in the trial are bound by this confidentiality clause.

13.11 Publication policy

The results of the trial will be published as soon as the data for the primary endpoint is available, initially as a poster/presentation at a congress, and then as a full publication in an international cardiology/heart failure journal. Draft manuscripts of publications will be prepared in co-operation between Endotronix and the Coordinating Investigator/Investigator(s). Joint publications are only possible if all parties agree. All editorial decisions will be made jointly by Endotronix and the Coordinating Investigator/Investigator(s).

Endotronix reserves the right to review any publication pertaining to the trial before it is submitted for publication. Neither party has the right to prohibit publication unless publication can be shown to affect possible patent rights or regulatory submission requirements.

In case of discrepancies with other contracts, the provisions of the protocol shall prevail.

13.12 End of Investigation /Premature Termination /Suspension

For EU only: In accordance with the Article 77(1) the end of this trial or, if applicable, a temporary halt or early termination of the trial will be reported to the national CAs of the participating European member states within the timelines stipulated in Article 77(3 and 4) of the MDR (Regulation (EU) 2017/745).

13.13 Final report

A final report, integrating medical and statistical aspects, will be prepared. This will be authorized by the relevant personnel of Endotronix, and the Investigators. The Investigator(s) will be provided with a copy of the summary of the final report. Endotronix will provide the FDA/ CAs and IRBs/ IECs with the complete clinical trial report within 1 year after the end of the trial or on request, where required.

13.14 Organization/ Site personnel

It may be necessary to define additional site personnel (e.g., doctors, nurses, technicians) who have a special responsibility for the performance of portions of the trial at a site under the auspices of the Investigator. The information regarding all site personnel taking part in the trial will be documented and stored in the Investigator's site file.

14 APPENDICES

14.1 Time and Event Schedule

Assessment	V1: Screening/ Enrollment (30 days) ¹⁵	V2: Cordella PA Sensor Implant Visit	V3: Month 1 (±7 days)	V4 ¹¹ : Month 3 (±7 days)	V5: Month 6 (±14 days)	V6: Month 12 (±30 days)	V7 to V8: Months 18, 24 (±30 days)	V9 to V11 Year 3, 4, 5 (±30 days)
Informed Consent	X							
Subject Demographics	X							
Study Eligibility Review and Committee Approval	X							
Cardiac/Medical & Surgical History	X							
Physical Exam, height, weight, and vital signs ^{1,5}	X	X	X ¹²		X	X	X	X
12-Lead ECG with Interpretation	X				X	X	X ⁴	X
Urinalysis ²	X							
Safety Labs (Chemistry/Hematology/ aPTT/ INR)	X				X	X	X ⁴	X
Serum NT-pro BNP	X		X	X ¹²	X	X	X	X
aPTT/ INR (if indicated)								
Echocardiogram ³	X					X		X
Subject Training: Cordella™ HF System ¹⁴	X							
Subject Training: CorPASS		X						
Cordella™ PA Sensor Implant		X						
Cordella System Use (daily)	X	X	X	X	X	X	X	X
Cordella™ PAP – dia/sys/mean/pulse		X ⁹	X ^{5,6}	X ^{5,6}	X ^{5,6}	X ^{5,6}	X ^{5,6}	X ⁶
RHC PAP / RAP/ PCWP/ CO/ CI/ RVP ⁸		X						X ¹⁷
Subject Status	X		X	X	X ¹⁰	X ¹⁰	X	X
6- Minute Walk Test	X				X	X ⁷	X ^{4,7}	X ⁷
NYHA Functional Classification	X ¹⁶		X	X	X	X	X	X
KCCQ Quality of Life Questionnaires ⁵	X		X	X	X	X	X	X
Concurrent/Cardiac Medications	X	X	X	X	X	X	X	X
Adverse Events	X	X	X	X	X	X	X	X
Health Economic Questionnaire							X ⁴	
Subject Survey (optional)/ Cohort #1 only ¹³	1. Month 1 after Unblinding 2. Quarterly until V11 / Year 5							
Site Survey (optional)/ Cohort #1 only ¹³	1. Month 1 after Unblinding 2. Quarterly until V11 / Year 5							


1. Full Physical Examination and Height performed at Screening Visit only2. Urine (V1) pregnancy test for females3. Echo may be obtained within 3 or 6 months of Screening details are in section 8.1.104. At Month 24 only5. via myCordella™ Patient App at home prior to visit. Baseline KCCQ will be completed on myCordella tablet following Cordella System distribution at Screening Visit6. via myCordella™ Patient App seated and supine7. Additional PAP Measurements will be obtained before and after 6-minute walk test8. Additional RHC as needed for Re-calibration purposes at the clinician's discretion	
9. Via CalEQ10. Incl. question on assigned treatment at Visit 5 and 611. Visit should be completed remote/ virtually12. If available13. After subject gets unblinded to PAP Pressures at V6 or cross-over whatever comes first14. Subject training on and distribution of the commercial Cordella™ System (should occur at Screening Visit (Visit 1).15. Some study procedures need to be repeated in case a subject is implanted >30 days after Visit 1, details are in section 8.3.1.16. may be obtained within the 30 day Study Visit 1 window17. At V9/ Year 3 only
---	--

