8.3 Schedule of Observations and Procedures

8.3.1 Study Visit 1 (Screening/ Enrollment Visit)

Subjects will be screened against entry criteria, and if confirmed to meet all requirements for enrollment and sign/date the current IRB approved consent, will be eligible for implant and enrollment into the study. The screening log will be maintained per Section 8.3.2

Written ICF must be provided by the subject prior to any study procedures being conducted, including screening labs or tests of any kind. Subjects will be screened against the inclusion and exclusion criteria and, if confirmed to meet all requirements, will then be enrolled into the study.

The following study procedures will be performed during this visit:

- Informed Consent
- Subject Demographics

- Study Eligibility Review
- Cardiac/Medical & Surgical History
- Physical Examination
- Height, Weight and BMI
- Vital Signs: BP, HR, SpO2
- 12-Lead ECG
- Safety Labs (Chemistry & Hematology & Urinalysis)
- Urine Pregnancy Test (female), if applicable
- Serum NT-pro BNP
- aPTT/INR (if indicated)
- Echocardiogram (may be obtained within 3 months of Screening)*
- NYHA Functional Classification (may be obtained within the 30 day Study Visit 1 window)
- 6-Minute Walk Test
- KCCQ Quality of Life Questionnaires
- Concurrent/Cardiac Medications
- Set Up/Subject Training: Cordella™ HF System (myCordella™ Tablet & Peripherals)*

*While an echocardiogram within 3 months of the screening visit date is preferable. In case this is not possible, Endotronix will accept an echocardiogram from within 6 months of Screening provided the patient does not have a standard of care indication for an echocardiogram during this interval.

After the subject has been approved by the PROACTIVE-HF Clinical Eligibility Committee, they will be enrolled into the study and can be scheduled for Study Visit 2 (Implant Visit).

In case a subject will be implanted >30 days after Study Visit 1, the following study procedures will need to be repeated and results obtained prior to implant:

- Reconfirm Study Eligibility Review
- Any changes in Health Status
- Any changes in concomitant medications
- Repeat selected Safety Labs

Hematology	Biochemistry	Urinalysis	
Hemoglobin	Sodium	Glucose	Nitrite
Hematocrit	Potassium	Protein	Blood
Leucocytes	Creatinine	Specific gravity	Leukocytes
Platelets	BUN	pH	
Lymphocytes	SGOT (AST)	Ketones	
aPTT/ INR	SGPT (ALT)	Bilirubin	
INR	GFR	Urine Pregnancy Test (females)	

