9 ADVERSE EVENTS

From the time of enrollment, at each evaluation of a subject enrolled in the trial, the investigator or site staff determines whether any adverse events (AE) have occurred and determines their relationship to the study devices or procedures. All adverse events, study device malfunctions and other product issues must be recorded in the appropriate eCRF section(s).

Safety will be assessed throughout the study by the frequency of Adverse Events (AEs), pressure sensor failure rate, and device/system-related complications by relationship to the device and severity. Additional emphasis on safety for the primary safety endpoint will be placed through 6 month following the Cordella PA Sensor Implant procedure to capture any adverse events associated with use of the Cordella PA Sensor.

Adverse events may be volunteered spontaneously by the subject, or discovered as a result of general, non-leading questioning. If it is determined that an AE has occurred, the investigator should obtain all the information required to complete the AE page of the eCRF, in accordance with the guidelines that accompany it. The investigator must submit to sponsor (or designee) any UADEs, and SAEs occurring during the study within 24 hours after being notified of the event and provides additional information, if required by Endotronic.

All AEs must be followed until resolution, until the condition stabilizes, until the event is otherwise explained or is judged by the investigator to be no longer clinically significant, or until the subject is lost to follow-up. The investigator is responsible for ensuring that follow-up includes any supplemental investigations necessary to elucidate as completely as practical the nature and/or causality of the AE. This may include additional laboratory tests or investigations, histopathological examinations, or consultation with other health care professionals.

Investigators are not obligated to actively seek AEs in former study participants. However, if the investigator learns of any SAE, including a death, at any time after a subject has been discharged from the study, and he/she considers the event reasonably related to the investigational product or study participation, the investigator should promptly notify Endotronic.

All AEs will be collected until a subject's participation in the trial is considered complete.

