3.4. Secondary Safety Endpoints

1. Pressure sensor failure rate throughout the study
2. Frequency of serious adverse events throughout the study
3. Frequency of implant procedure and procedure related adverse events and serious adverse events

This document is confidential.

4. Analysis Sets

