5.2. Key Definitions

Age

Age at screening is derived in the database and this value will be used for all analyses.

Definition of Baseline for safety assessments

Baseline will be defined as the last available value prior to the implant of Cordella PA Sensor and may be at any visit between Screening (V1) and Cordella PA Sensor Implant Visit (V2).

Definition of Baseline for PAP measurements

Baseline will be defined as value at Implant Visit (V2) obtained before discharge .

Change from Baseline

Absolute change from baseline:

Absolute change = Post-baseline value –baseline value

Time to Onset of AE

Time to onset of AE [days] = Date of start of AE – Date of implant of Cordella PA Sensor + 1

Start Day of concomitant medication

If medication starts before date of implant of Cordella PA Sensor:

Start Day of Medication = Date of start of medication – Date of implant of Cordella PA Sensor

If medication starts at/after date of implant of Cordella PA Sensor

Start Day of Medication = Date of start of medication – Date of implant of Cordella PA Sensor + 1

Incomplete start dates of medication will not be imputed. Start day of medication will be missing.

Stop Day of concomitant medication

If medication stopped before date of implant of Cordella PA Sensor:

Stop Day of Medication = Date of end of medication – Date of implant of Cordella PA Sensor

If medication stops at/after date of implant of Cordella PA Sensor

This document is confidential.

Stop Day of Medication = Date of end of medication – Date of implant of Cordella PA Sensor + 1
Incomplete end dates of medication will not be imputed. Stop day of medication will be missing.

Definition of study completed/discontinued/ongoing

A subject will be defined as study ‘completed’/‘discontinued’ based on the eCRF information. At the time of the pre-defined main analysis, subjects which are ongoing at date of cut-off will be counted as ‘ongoing’.

Time since first diagnosis of heart failure

Time since diagnosis [months] = ((Date of Screening – Date of first HF diagnosis)+1)/30

Exposure time:

which would be exact 6 or 12 months (180 or 365 days respective) post-implant visit for subjects who are still in the study at/after this timepoint.

which would be [date of last available date – date of Implant visit + 1] for subjects who withdraw from study prior to month 6 or 12 (180 or 365 days respective) post-implant visit.

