8.3. Adverse Events

All collected adverse events (AEs) will be coded using MedDRA, version 24.0, to give a preferred term and a SOC term for each event and used for the analysis.

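### The general AE and SAE tables have no onset rule, so events from the wait before implant are mixed with events after the procedure without being labelled

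*Protocol*

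**What the plan says.** **Start of collection.** Protocol Section 9 has the site look for adverse events "From the time of enrollment, at each evaluation of a subject enrolled in the trial". Section 8.3.1 places enrollment before implant: "After the subject has been approved by the PROACTIVE-HF Clinical Eligibility Committee, they will be enrolled into the study", and only then is the implant visit scheduled. In Appendix 14.1 the Adverse Events row is marked at every visit, including the one headed "V1: Screening/ Enrollment (30 days". The list of Visit 1 procedures in 8.3.1, however, has no adverse event item; the first list that has one is for Visit 2 (8.3.2).

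**Length of the wait.** Implant more than 30 days after Visit 1 is foreseen, with repeat checks: "In case a subject will be implanted >30 days after Study Visit 1" in 8.3.1, and footnote 15 of 14.1, "Some study procedures need to be repeated in case a subject is implanted >30 days after Visit 1". Section 4.2 expects that subjects will typically have used the Cordella System for about a week before implant; under 8.1.15 that system is handed out at Visit 1.

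**What is tabulated.** SAP 8.3 has all collected events coded to give "a preferred term and a SOC term for each event and used for the analysis". SAP 1.2 says summaries that are not by visit, adverse events included, take everything up to the cut-off date. SAP 8.3.4 lists the tables without an onset condition. Secondary safety endpoint 2 in SAP 3.4 is "Frequency of serious adverse events throughout the study". The tables use the ITT set, which SAP 4.2 limits to enrolled subjects who reached the Cath Lab, implanted or not.

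**Onset.** SAP 5.2 defines "Time to onset of AE [days] = Date of start of AE" minus the implant date plus 1. It has no separate branch for events before implant.

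**The concern.** In a single-arm device study the AE tables have no control arm to absorb background events, so the reader needs to know which period they cover. Heart failure and bleeding are both predefined categories in SAP 8.3.3. A heart failure admission between enrollment and implant would enter the same SAE count as one a month after implant, and nothing in the table would tell them apart.

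This looks like an omission rather than a choice, because the SAP divides time at implant almost everywhere else: medication start and stop days (5.2), baseline against concomitant medication (6.5.1 and 6.5.2), HF hospitalizations before and after implant (7.1.5), the primary event rate (7.1.1) and the primary safety clock (8.1.1). Only the general AE tables lack such a rule. What is at stake is how a descriptive secondary safety endpoint and its supporting tables are read, not a test result.

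**Working it through.** The documents give no expected overall AE or SAE frequency, so there is no figure of the plan to reproduce. The check has two parts.

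**1. Does any rule remove pre-implant events?**

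- Protocol Section 9 with 8.3.1: recording starts at enrollment, which comes before implant.
- SAP 8.3 and 1.2: all collected events are used, with an end limit only.
- SAP 8.3.4: no table has an onset condition, and neither document defines a treatment-emergent or procedure-emergent event.
- SAP 5.2: the onset formula excludes nothing. An event the day before implant gets −1 + 1 = 0, and one two days before gets −2 + 1 = −1. For ITT subjects who were never implanted there is no implant date to put in.
- SAP 8.1.1 and 7.1.1: both primary safety endpoints and the primary efficacy rate are counted from the implant visit, so they do have a time origin.

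The gap therefore exists, and it is confined to the general AE and SAE tables and secondary safety endpoint 2.

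**2. How large could it be?** Inputs:

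- Follow-up of 180 days after implant: the SAP 5.2 value for 6 months.
- Pre-implant gap d: 7 days (the typical week in protocol 4.2), 30 days (the Visit 1 column in 14.1), and 14 and 45 days (assumed).
- Proportion p of subjects with at least one SAE in the 180 days after implant: assumed, 20% to 50%.
- Constant hazard before and after implant: assumed.

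Pre-implant share of the time to Day 180 = d/(d + 180). Proportion shown without an onset rule = 1 − (1 − p)^((180 + d)/180).

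| d (days) | Share of time | p = 20% | p = 30% | p = 40% | p = 50% |
|---|---|---|---|---|---|
| 7 | 7/187 = 3.7% | 20.7% | 31.0% | 41.2% | 51.3% |
| 14 | 14/194 = 7.2% | 21.4% | 31.9% | 42.3% | 52.6% |
| 30 | 30/210 = 14.3% | 22.9% | 34.0% | 44.9% | 55.5% |
| 45 | 45/225 = 20.0% | 24.3% | 36.0% | 47.2% | 58.0% |

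The planned tables run to the cut-off, not to Day 180. The share falls to 7/372 = 1.9% (7 days) or 30/395 = 7.6% (30 days) at one year, and to 7/1102 = 0.6% or 30/1125 = 2.7% at three years. With the hazard that gives 40% by Day 180, the three-year proportion is 1 − 0.6^(1095/180) = 95.5%. Adding 30 pre-implant days makes it 1 − 0.6^(1125/180) = 95.9%.

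**The case against.** The strongest defence is that an endpoint covering the whole study, with recording from enrollment, includes the waiting period by its own terms. The affected outputs are descriptive, with no formal test. This stands in part: collecting events from enrollment is sound practice, and including them is a possible choice. What is missing is a statement of that choice and a way to separate the two periods.

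A reader might also infer more than the documents support:

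- *That the SAE frequencies are materially inflated.* The one indication of a typical gap is about a week. Enrollment follows Visit 1, so the Visit 1 gap is a ceiling on the exposed time. Entry requires clinically stable patients, and follow-up at the cut-off is often well beyond 180 days. All of this points to the low end of the range.
- *That waiting-period events are attributed to the device.* They are not. SAP 8.3.4 has separate tables for device/system-related complications, UADEs, and study-procedure-related and implant-procedure-related events.
- *That deaths before the Cath Lab disappear.* They are absent from the ITT tables, but the death and SAE listings in the SAP index use the Enrolled set, so they stay visible.
- *That the wait is uncontrolled.* No maximum is stated, but beyond 30 days eligibility must be reconfirmed, and health status, medication and selected labs checked again before implant.
- *That the results cannot be compared with other device studies.* The documents do not give the counting rules of those studies, so this cannot be judged.

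One further point cuts both ways. Protocol 8.1.6 updates the medical history just before the procedure, so a waiting-period event could be recorded as history, as an AE, or as both. That may lower the count, but it also makes the content of the tables less certain.

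**Conclusion.** The gap is real and its priority is low. Followed as written, the SAP puts pre-device events into secondary safety endpoint 2 and the overall, SOC/PT, severity and predefined-category AE and SAE tables, in a set restricted to subjects who reached the Cath Lab. Those frequencies then do not belong to one defined risk period. It would be too strong to call them wrong.

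For a 40% SAE proportion by Day 180, the excess is about 1 percentage point with a 7-day gap and about 5 points with a 30-day gap, and it declines with longer follow-up. These figures rest on an assumed SAE proportion and a constant hazard. Of the gaps used, only 7 and 30 days have any basis in the documents, so the true size cannot be determined from them. The primary safety and primary efficacy conclusions do not change.

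**What to change.** In SAP 8.3:

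1. Add a flag for AEs with onset on or after the date of the implant procedure. For ITT subjects who were not implanted, use the date of the Implant Visit, because SAP 5.2 has no date for them. Count same-day events of unknown time as on or after.
2. Base secondary safety endpoint 2 and the general AE and SAE tables on flagged events.
3. Show AEs with onset from enrollment up to the procedure in one separate table and one listing, so that nothing is hidden.
4. Keep study-procedure-related, implant-procedure-related and device-related events in their own tables whatever the onset date. Otherwise an event tied to protocol-directed preparation, such as the interruption of anticoagulation before the implant visit described in 8.1.22 and 8.3.2, would drop out of the table where it belongs.

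In the protocol, reconcile 8.3.1 with 14.1 and Section 9 on when AE collection starts.

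The cost is one derived flag, one extra table with its listing, and a few sentences. The flag uses event and visit dates that the SAP already relies on, so no new data are needed.
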